8.2 Recording of Adverse Events

All adverse events occurring during the study, including those not meeting the criteria of an Unanticipated Adverse Device Effect (UADE) will be recorded on the appropriate case report form on the day of the occurrence. Records of these events will be maintained and reports submitted to the FDA and IRB according to the regulatory requirements. Expected clinical adverse events and nonsignificant (not serious) clinical adverse events will not be reported. Expected clinical adverse events and anticipated adverse device effects are those listed in Section 1.4.1. The PI/Sponsor ([name]) and research team will follow all AEs, SAEs, and other reportable events until the event has subsided or values have returned to baseline, or in case of permanent impairment, until the condition stabilizes.

8.3 Reporting Procedures

At each required study visit, all AEs that have occurred since the previous visit will be recorded in the adverse event record of the Participant's CRF. The information recorded should be based on the signs or symptoms detected during the physical examination and clinical evaluation of the

Participant. In addition to the information obtained from those sources, the Participant should be asked the following nonspecific question: "How have you been feeling since your last visit?" Signs and symptoms should be recorded using standard medical terminology. On the case report form the treating physician will record the event, sign with their initials and enter the current date. After the treatment is completed, this process will be repeated. The PI or a Co PI will review the Adverse Events on a daily basis and will determine the event to be "Clinically Significant" or "Not Significant." This process can be completed by phone, email or face to face.

The following AE information must be included (when applicable): the specific condition or event and direction of change; whether the condition was preexisting (i.e., an acute condition present at the start of the study or history of a chronic condition) and, if so, whether it has worsened (e.g., in severity and/or frequency); the dates and times of occurrence; severity; causal relationship to the investigational device; action taken; and outcome.

Causal relationship options and definitions are as follows:

- *Definitely related*: Event can be fully attributable to administration of the investigational device.
- *Probably related*: Event is most likely to be explained by administration of the investigational device, rather than the Participant's clinical state or other agents/therapies.
- *Possibly related*: Event is as likely explained by administration of the investigational device, as by the Participant's clinical state or other agents/therapies.
- *Probably not related*: Event is most likely to be explained by the Participant's clinical state or other agents/therapies, rather than the investigational device.
- *Definitely not related*: Event can be fully explained by the Participant's clinical state or other agents/therapies, rather than the investigational device.

When assessing the relationship between an investigational product/protocol and an AE, the following parameters are considered:

- Temporal relationship between the investigational device/protocol and the AE
- Biologic plausibility of relationship
- Participants' underlying clinical state or concomitant agents/therapies
- Where applicable, whether the AE abates on discontinuation of the investigational device (dechallenge)
- Where applicable, whether the AE reappears on repeat exposure to the investigational device (rechallenge)

SAEs that are not investigational device-related may nevertheless be considered by the participating Investigator or the medical monitor (or designee) to be related to the conduct of the clinical study, i.e., to a Participant's participation in the study.

For this study, the treatment follow-up period for adverse events is defined as 30 days following the last study visit. Follow up will be documented in the Participants study file.

Per Mayo Clinic policy: “All health care providers in the State of Minnesota are mandated reporters under the Minnesota Maltreatment of Minors Act.” All study staff are made aware of this policy and will remain in compliance with associated reporting procedures when necessary.

8.3.1 Sponsor-Investigator Reporting, Notifying Mayo IRB

The sponsor-investigator will report to the Mayo IRB any UPIRTSOs and Non-UPIRTSOs according to the Mayo IRB Policy and Procedures.

8.3.2 Sponsor-Investigator Reporting: Notifying the FDA

The sponsor-investigator will report to the FDA all unanticipated adverse device effects according to the required reporting timelines, formats and regulations.

Additionally, per FDA request, all blurred vision adverse events will be reported to the FDA within 5 business days.

The sponsor-investigator will submit a completed **FDA Form 3500A** to the FDA’s Center for Devices and Radiological Health for any observed or reported adverse effect that is determined to be an unanticipated adverse device effect. A copy of this completed form will be provided to the DSMB and all participating sub-investigators.

The completed FDA Form 3500A will be submitted to the FDA as soon as possible and, in no event, later than 10 working days after the sponsor-investigator first receives notice of the adverse effect.

If the results of the sponsor-investigator’s follow-up evaluation shows that an adverse effect that was initially determined to not constitute an unanticipated adverse device effect does, in fact, meet the requirements for reporting; the sponsor-investigator will submit a completed FDA Form 3500A as soon as possible, but in no event later than 10 working days, after the determination was made.

For each submitted FDA Form 3500A, the sponsor-investigator will identify all previously submitted reports that that addressed a similar adverse effect experience and will provide an analysis of the significance of newly reported adverse effect in light of any previous, similar report(s).

Subsequent to the initial submission of a completed FDA Form 3500A, the sponsor-investigator will submit additional information concerning the reported adverse effect as requested by the FDA.

Reporting Process

Unanticipated Adverse Device Effect reports will be submitted on FDA Form 3500A. The contact information for submitting reports is:

Food and Drug Administration
Center for Devices and Radiological Health
Document Mail Center - WO66-G609
[name]
Silver Spring, Maryland 20993-0002

8.3.3 Deviations from the investigational plan.

The sponsor-investigator shall notify Mayo IRB (see 21 CFR 56.108(a) (3) and (4)) of any deviation from the investigational plan to protect the life or physical well-being of a Participant in an emergency. Such notice shall be given as soon as possible, but in no event later than 5 working days after the emergency occurred. Except in such an emergency, prior approval by the sponsor-investigator is required for changes in or deviations from a plan, and if these changes or deviations may affect the scientific soundness of the plan or the rights, safety, or welfare of human Participants, FDA and IRB notification in accordance with 21 CFR 812.35(a) also is required.

8.4 Unblinding Procedures (Breaking the Blind)

While the safety of the participant always comes first, it is still important to seriously consider if unblinding the study therapy is necessary to ensure a Participant's safety. In the event of a serious adverse device effect, the Investigator will carefully assess whether breaking the blind will critically affect how a Participant is treated in response to the adverse effect and whether this knowledge outweighs the implications to the scientific soundness of the study. In the case of most serious adverse effects, treatment would be discontinued and symptoms treated symptomatically. In these instances, having this information would not significantly alter the treatment of the adverse effect(s).

As an additional safeguard against bias, the DSMB has been charged with making the final recommendations for breaking the study blind

If the decision to break the blind is made immediately upon learning of the adverse event, this information will be reported to the FDA and reviewing IRB at the time of initial adverse event reporting. If the unblinding occurs after the initial reporting, the FDA will be notified of the action within ten working days from the time of breaking the blind. The reviewing IRB will be notified according to their reporting guidelines if the decision is made to break the study blind after the initial reporting.

8.5 Stopping Rules

Specific occasions when study treatment may be stopped are explained Section 4.4.1 in the discussion of Anticipated Risks.

Because of the anticipated low level of adverse events of TMS, the DSMB will be charged with reviewing adverse events at least every six months. Serious adverse events will be reviewed on a monthly basis, unless a more urgent review is requested. Only under extreme circumstances or if it were determined that a high level of side effects was due to TMS, would the DSMB be charged with breaking the study mask.

Specific Study Stopping Rules

The study will be stopped should any of the following occur:

- Two participants experience seizures
- One or more participant experiences status epilepticus
- One or more participant attempts or commits suicide during treatment weeks in Phase I or II.
- Two or more Serious Adverse Events in one or more participants.
- Two or more participants have blurred vision associated with rTMS treatment (confirmed by an ophthalmologist.)

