Potential for unintended behavioral change: (e.g., worsening of depression or induction of mania): Crying has been reported in some patients receiving left prefrontal rTMS. There is no evidence to suggest that a frank worsening of depression may be seen in patients with major depression receiving rTMS. On the other hand, mania has been observed in bipolar disorder patients who have received rTMS.^{38,74,75} [name] and the study team will be available 24 hours a day to address any concerns participants or families have regarding changes in behavior. Adverse events are monitored at every treatment visit. [name] or a board-certified child and adolescent psychiatrist will remain in the neurostimulation suite (in a room adjacent to the rTMS treatment room) during all rTMS treatment sessions.

Suspected treatment-induced mania will be evaluated using the Young Mania Rating Scale (YMRS). A YMRS score of ≥ 20 will prompt administration of the M.I.N.I.(age 18) or M.I.N.I. KID to determine whether or not the Participant meets the Diagnostic and Statistical Manual of Mental Disorders, Fifth Edition (DSM-5) criteria for mania. A YMRS score of 20 or greater will be considered an adverse event (AE) and will be monitored using the YMRS; the emergence of DSM-5 verified mania will be treated as a serious adverse event (SAE) and will also be monitored using the YMRS.

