4.4 Early Withdrawal of Participants

4.4.1 Participant Withdrawal, Data Collection, and Follow-Up

Participants may withdraw voluntarily from the study at any time. Participants will be withdrawn from the study by the PI/Sponsor if a participant:

- experiences a seizure,
- experiences a DSM-5-confirmed treatment-induced mania,
- is non-compliant with study procedures; or
- endorsed illicit drug use or has a positive urine drug screen during the study

The PI may also withdraw a participant if he/she believes that for safety reasons it is in the best interest of the participant to be withdrawn.

Discontinuation information [e.g., date and the reason(s) for discontinuation] will be recorded in the Participant's CRF (Case Report Form). Participants who discontinue prematurely should complete the Week 6 assessment procedures within 2 days following their last TMS treatment session. See the Schedule of Events for the specific procedures to be performed at this discontinuation visit.

Participants withdrawn from the study due to an AE will be followed up for 30 days or until resolution. Participants withdrawn from the study will not be replaced, regardless of the reason for withdrawal. An effort will be made to determine why a participant does not return for the required visits or is dropped from the study. This information will subsequently be recorded on the participant's CRF. Participants will be encouraged to remain compliant with all expected study visits. Non-adherence to expected study visits will be documented and may result in removal from the study. This will be clearly discussed during the consent/assent process and reinforced throughout the study through regular screening for issues with compliance.

[name] will assist with clinical referral for all participants who voluntarily withdraw from the study or are withdrawn by the research team and PI. Specifically, [name] will offer ongoing clinical care or community referrals based on the preference of the participant.

5 Study Device

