8.6 Medical Monitoring

The PI/sponsor ([name]) has oversight and accountability for the overall safety of the study participants. PI/sponsor safety monitoring will include careful assessment and appropriate reporting of adverse events as noted above, as well as the construction and implementation of a data and safety-monitoring plan. Medical monitoring will include a regular assessment of the number and type of serious adverse events.

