8.6.1 Independent Data and Safety Monitoring Board

A Data and Safety Monitoring Board will be assembled to oversee the safety of the study, Participants, and the scientific validity and integrity of data collected as part of the study. This DSMB will include members from academic sites independent of the study sites and will consist of at least one non-study, board-certified psychiatrist and one biostatistician.

The responsibilities and decision points for the DSMB will be captured in the DSMB charter.

9 Data Handling and Record Keeping

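### Two serious adverse events of any cause require the study to stop, and the stop is not conditional on the DSMB review that the same section provides

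*Combined protocol and SAP*

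**What the plan says.** Section 8.5 makes a stop mandatory if any of five events occurs. The fourth is "Two or more Serious Adverse Events in one or more participants". Both events may fall in one participant.

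Two neighbouring rules carry limits. One reads "Two or more participants have blurred vision associated with rTMS treatment" and needs confirmation by an ophthalmologist. The other reads "One or more participant attempts or commits suicide during treatment weeks in Phase I or II". The seizure and status epilepticus rules carry no such limits, but each names a specific harm.

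On oversight, Section 8.5 says "Serious adverse events will be reviewed on a monthly basis, unless a more urgent review is requested", and Section 8.6 adds "Medical monitoring will include a regular assessment of the number and type of serious adverse events". Section 8.6 also provides for a data and safety-monitoring plan. Section 8.6.1 says "The responsibilities and decision points for the DSMB will be captured in the DSMB charter". Neither the plan nor the charter is among the documents.

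Section 8.1 defines adverse events without regard to cause, treats an admission as serious, and resolves doubt in favour of calling an event an SAE. It excludes elective and pre-planned admissions, and admissions for the target disease that the investigator does not judge to be a worsening.

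**The concern.** The trigger counts events of any kind and any cause, and it leads to a stop and not to a decision. The trial enrols depressed adolescents, and Section 1.5.2 makes those with current suicidal ideation eligible, so admissions for worsening illness or for unrelated reasons are foreseeable. Verified mania is also an SAE under Section 1.5.2, although the planned response in Section 4.4.1 is to withdraw that one participant. One such case plus one unrelated admission would meet the rule.

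The rule also sits awkwardly with the oversight around it. Only one SAE in the whole study can be reviewed before a stop is due. If two fall between monthly reviews, the stop is due before the DSMB has seen either. The five-level causality rating in Section 8.3 plays no part.

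At stake are an interruption or end of the trial that says nothing about the safety of rTMS, and broken treatment courses for those in mid-course. After a second SAE, the sponsor would have to follow a rule that may be uninformative or depart from a written safety rule in a vulnerable population.

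**Working it through.** **Step 1: what the rule conditions on.** Set against the other rules in Section 8.5:

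| Rule | Specific harm named | Relation to rTMS required | Period stated | Stop conditional on DSMB review |
|---|---|---|---|---|
| Two seizures | yes | no | no | no |
| Status epilepticus | yes | no | no | no |
| Suicide or attempt | yes | no | treatment weeks | no |
| Blurred vision | yes | yes, and confirmed | no | no |
| Two SAEs | **no** | **no** | **no** | **no** |

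The two-SAE rule is the only one that is open on all four counts.

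**Step 2: the counting period.** Two windows for adverse events exist elsewhere, and they differ. The Table 3 footnote runs from the first TMS session to 30 days after the last TMS session. Section 8.3 runs to 30 days after the last study visit, which takes in the 6-month follow-up. Section 8.5 refers to neither, so two readers could disagree on whether the rule has been met.

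**Step 3: how sensitive the rule is.** The plan gives no expected SAE rate and no operating characteristic for the rule, so there is no figure to reproduce. Inputs:

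- n = 120 participants (Section 3.1).
- Rates of 0.5%, 1% and 2% per participant. These are assumptions.
- Poisson count of all SAEs, which allows two in one participant. With m = n × rate, P(two or more) = 1 − e^(−m) × (1 + m).

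Results:

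- 0.5%: m = 0.6; 1 − e^(−0.6) × 1.6 = 0.122
- 1%: m = 1.2; 1 − e^(−1.2) × 2.2 = 0.337
- 2%: m = 2.4; 1 − e^(−2.4) × 3.4 = 0.692
- P = 0.50 at m = 1.678; 1.678 / 120 = 1.40%

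An exact binomial count of participants with an SAE gives nearly the same: 12.2%, 33.8%, 69.5%, and 50% at 1.395%. With n = 100 (the evaluable target) the Poisson figures are 9.0%, 26.4% and 59.4%, but 120 is the better denominator because participants who drop out can have SAEs too. No separate allowance is made for Phase II exposure, which would raise the figures.

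**Step 4: what these figures are not.** They cover a stop at any time, including late in the study. At the 50% point, if events accrue evenly, the chance of meeting the rule in the first half of exposure uses m = 1.678 / 2 = 0.839: 1 − e^(−0.839) × 1.839 = 0.205, or about 20%.

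**The case against.** The strongest reply has four parts.

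*A strict, cause-blind trigger is a reasonable choice in adolescents.* This stands. Counting every SAE avoids arguments about cause when an alarm is raised, and the fix keeps it. The mania example carries limited weight: Section 4.4.1 speaks of a participant who "experiences a DSM-5-confirmed treatment-induced mania", which a safety trigger should count, and Section 1.5.2 reports that the group has never seen emergent mania in an rTMS protocol.

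*The suicide rule is harsher, since one event stops the study, so changing only the two-SAE rule is arbitrary.* This stands in part. None of the rules has a review step. But the other four name specific serious or device-relevant harms, for which an automatic stop is easy to defend. The two-SAE rule covers any SAE.

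*The charter or the monitoring plan may say who reviews and who lifts a stop.* This stands as a limit on the point. Section 8.5 does not say whether a stop is permanent, and it may be meant as a halt pending review. Still, its wording is mandatory and refers to no such step.

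*The percentages have no documented rate to be compared with.* This stands. They describe the rule and forecast nothing.

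A reader might infer that SAEs go unreviewed, that every admission counts, or that no window exists anywhere. The documents support none of these. Section 8.5 provides SAE review, Section 8.1 excludes some admissions, and two windows are given, though they differ and the rule cites neither.

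**Conclusion.** The point holds as a weakness in a safety rule, worth a cheap improvement. As written, two SAEs in total require a stop whatever their cause, and the DSMB review available in the same section is not a condition of that stop. The counting window is unnamed, and the permanence of a stop and the authority to lift it are unstated in the documents supplied.

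Its practical size is unknown, because it depends on an SAE rate that the plan does not give; Section 8.5 itself expects few adverse events. Under the assumed rates and 120 participants, the chance of meeting the rule at some point runs from about 12% (0.5%) to 69% (2%), passing 50% near 1.4%.

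A reader might conclude that the trial is likely to be ended early, or that these are chances of falling short of 100 evaluable participants. Neither follows. No rate supports the first, and a stop late in the study need not cause the second. Nor do the documents show that a stop would permanently end anyone's treatment. The rule does not bias any estimate or test.

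**What to change.** Amend Section 8.5 so that two SAEs of any cause, including two in one participant, trigger an immediate pause of enrolment and TMS. The pause lasts until an urgent DSMB review, which the section already allows. The DSMB uses the causality rating and the relation to study conduct in Section 8.3, decides whether to stop or resume, and states the next trigger if it resumes.

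Name one counting window in the rule. Ending it 30 days after the last TMS session keeps the count close to treatment. Ending it 30 days after the last study visit is more cautious, but adds off-treatment months in which unrelated admissions would cause a pause.

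State in Section 5.7 that sessions missed in a pause are not non-adherence. That section limits gaps to 3 calendar days and counts three missed treatments in daily sequence as non-adherence, so even a one-week pause would breach it.

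Leave the seizure, status epilepticus, suicide and blurred-vision rules unchanged.

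The cost is one amendment with FDA and IRB review, and a check against the charter and the monitoring plan. No new data are needed. The downside is that a DSMB judgement replaces an automatic stop, and participants in mid-course lose sessions during a pause.

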8.6 Medical Monitoring

The PI/sponsor ([name]) has oversight and accountability for the overall safety of the study participants. PI/sponsor safety monitoring will include careful assessment and appropriate reporting of adverse events as noted above, as well as the construction and implementation of a data and safety-monitoring plan. Medical monitoring will include a regular assessment of the number and type of serious adverse events.

8.6.1 Independent Data and Safety Monitoring Board

A Data and Safety Monitoring Board will be assembled to oversee the safety of the study, Participants, and the scientific validity and integrity of data collected as part of the study. This DSMB will include members from academic sites independent of the study sites and will consist of at least one non-study, board-certified psychiatrist and one biostatistician.

The responsibilities and decision points for the DSMB will be captured in the DSMB charter.

9 Data Handling and Record Keeping

